### 11.4 COMPLIANCE & ADHERENCE

All vaccinations will be administered by clinically trained site staff to ensure compliance.

## 11.5 DOSE MODIFICATIONS, INTERRUPTIONS & DISCONTINUATIONS

There are no planned modifications to dose, other than discontinuation.

The schedule may be modified if a participant has symptoms or signs on the day of scheduled immunisation, and the investigator considers it best to defer the immunisation. The participant will be asked to return for review within the window period of a scheduled immunisation.

The Principal Investigator may decide to permanently discontinue dosing in a participant who has received one or more vaccinations, if it is deemed that continuing might compromise the participant's wellbeing or interfere with the achievement of the trial's objectives. Participants will be encouraged to continue to attend trial visits for sampling and safety monitoring.

Discontinuation of dosing is essential following a grade 3 or 4 clinical or laboratory event (confirmed on examination or repeat testing respectively) which is considered possibly, probably or definitely related to the vaccine and which did not resolve within 72 hours. All participants will be followed up for the duration of the study and samples will be collected at the allotted times.

Dosing must be discontinued in participants who become pregnant or HIV infected.

Participants may decide to discontinue dosing. They will be encouraged to provide a reason, and to remain in follow-up. If the participant explicitly states their wish not to contribute further data to the study, the PI should be informed in writing.

Both the PI and the coordinator centre should be informed as soon as possible if a participant chooses to stop receiving vaccines or to withdraw from the trial, and within 1 working day of a decision being taken to discontinue a participant when that decision is informed by an adverse event (**Section 13.1**).

## 11.6 CLINICAL MANAGEMENT OF ADVERSE EVENTS

Adverse events will be managed by the clinical trial team who will assess and treat the event as appropriate, including referral to an independent physician and/or the participant's General Practitioner if required. Clinically significant abnormalities detected following clinical examination or routine laboratory tests will be managed as determined by local PI or delegate.

## 11.7 NON-TRIAL TREATMENT

As stated in the exclusion criteria, participants should not have received other immunisations, blood products, immunoglobulin, immunosuppressive medicines or other trial medication within specified periods prior to enrolment. This applies during the trial through

to the final safety visit 28 weeks after enrolment, 4 weeks after the last scheduled immunisation, unless the treatment is required for an emergency.

Should a participant require immunisation for the purposes of travel, occupation or other clinical need during the trial, the request will be reviewed by the Principal Investigator who will advise on timing and whether or not the trial immunisation schedule needs to be amended.

Participants will be allowed to continue with hormonal contraception if this forms part of their regular appropriate contraception plan. Details will be recorded on the screening and concomitant medication CRF.

All concomitant medication will be recorded on the CRF, including any dispensed by the investigators in the management of adverse events or reactions.

### **11.8 ISSUES RELATED TO HIV**

A 4th generation HIV antibody/antigen assay, the standard laboratory method for diagnosing HIV infection, will be used to screen participants. An HIV test will be performed at two time-points in the study: the screening visit, and the final visit 48 weeks from enrolment. During the study clinic staff will determine whether the risk status for HIV has changed and repeat tests if necessary.

After completing the study, regardless of whether or not they are reactive in HIV tests, participants will be provided with appropriate certification of their HIV antibody status, and (if clinically indicated) invited to return to the clinical centre for re-testing until such time as the test becomes negative.

### **11.9 VERIFICATION OF HIV STATUS OF PARTICIPANTS**

In the event of an equivocal or positive result which the PI is not convinced to be vaccine-induced, a specimen will be processed through a range of assays according to the local laboratory operating procedures to establish the HIV status of the individuals. A confirmatory specimen will be collected at a later date, if the first result suggests that the participant is HIV infected.

### **11.10 HIV INFECTION**

In the unexpected circumstances that a participant in the trial acquires HIV infection, they will be referred for clinical care and counselling. Participants will be referred initially to a specialist physician for a full discussion of the clinical management of HIV infection. Further investigations will be undertaken as necessary. Should the participant prefer to be managed

at a hospital closer to their home, this will be arranged. Referral for counselling will be arranged by the specialist physician, to a counsellor at their clinical centre.

## 12 ASSESSMENTS & FOLLOW-UP

### 12.1 ASSESSMENTS AT SCREENING

#### 12.1.1 INFORMED CONSENT PROCESS

A site-specific Consent Form will be submitted and approved by the Independent Ethics Committee (IEC)/ Ethics Review Board (ERB).

#### Participant Information Sheet

A qualified member of the study staff will conduct the informed consent process by reviewing the Participant Information Sheet with the volunteer, and answering any questions. This process will be documented in the clinic notes.

#### Consent Form

The volunteer's consent to participate must be obtained by him/her signing and dating the Consent Form. The person obtaining consent will also sign.

The signed/marked and dated Informed Consent Document must remain at the study site. A copy of the signed/marked and dated Informed Consent Document, and PIS will be offered to the volunteer to take home.

#### 12.1.2 DEMOGRAPHICS, MEDICAL HISTORY AND PHYSICAL EXAMINATION

Demographic information such as age and ethnic origin will be collected at screening and entered onto the CRF.

A past and current medical history will be collected at screening during a face to face structured interview using a source document, such that relevant aspects of eligibility can be adequately assessed.

The general physical examination will include weight (kg), height (cm), calculation of BMI, temperature, blood pressure and heart rate (vital signs), inspection of the skin and respiratory, cardio-vascular, abdominal, and neurological systems. An assessment of cervical, axillary and inguinal lymph nodes will also be undertaken.

#### 12.1.3 HIV RISK ASSESSMENT & SEROLOGY TESTING

An HIV risk assessment will be performed according to the relevant eligibility criterion.

The following will be collected from all participants:

- Serology for HIV and syphilis
- Serology for markers of hepatitis B and hepatitis C infection
- Urine for Chlamydia and gonorrhoea at screening
- Serology for Ad4 neutralising antibodies
- Serology for antinuclear antibodies and immunoglobulins IgA, IgG and IgM

#### 12.1.4 ROUTINE LABORATORY PARAMETERS

Peripheral blood will be collected by trained staff into the appropriate containers and transported to the local laboratory.

All laboratory assessments, except urine pregnancy tests which will be done by the trained individuals on site, will be done by the local laboratory.

The following parameters will be collected from all participants:

- Hb, total WBC, neutrophils, lymphocytes and platelets
- creatinine, total bilirubin, alkaline phosphatase (ALP) and alanine aminotransferase (ALT)
- Urine test (female participants) to exclude pregnancy

#### 12.2 VACCINATION AND FOLLOW-UP VISITS

- The assessments that will be performed at each visit are described in Table 2.
- Participants will be required to make 11 scheduled outpatient visits over the course of 48 weeks. Time 0 will start on the day of enrolment, which is also the day of randomisation and the first immunisation, and must be within 90 days after screening.
- Vaccinations will take place at Weeks 0 (Month 0), 12 (Month 3) and 24 (Month 6).
- Serum and peripheral blood mononuclear cells (PBMC) will be collected for immunogenicity at Weeks 0 (enrolment), 4, 12, 16, 24, 25, 26, 28 and 48.
- Adverse events will be assessed during the enrolment visit before and after immunisations and at every visit thereafter until the final safety visit at Week 28; thereafter only serious adverse events will be recorded.
- Injection sites will be inspected vaccination days at Weeks 12 and 24 (pre-dose and 60 (+/-10) min post-dose), and at Weeks 13 and 25.
- Symptom-directed physical examinations will be done at Week 0 and at every visit thereafter until the final safety visit at Week 28.
- Vital signs will be done on vaccination days (pre-dose and 60 (+/-10) min post-dose) and at Weeks 1, 13, 25, 26 and 28.
- Concomitant medications will be collected at every visit up to the final safety safety visit.
- Blood for routine laboratory safety parameters will be collected at Weeks 0 (enrolment), 1, 12, 13, 24, 25, 26 and 28 and at any other visit if clinically indicated.
- Mucosal samples for antibody responses (genital / rectal / nasal) will be collected at Weeks 0, 4, 12, 16, 24, 26 and 48.
- Urine pregnancy test will be assessed at Weeks 0, 12, 24 and 28.
- Rectal swabs for Ad4-EnvCN54 PCR will be assessed at Weeks 0, 1, 4, 13, 16, 25, 26, 28 and 48.

- Rectal biopsies will be assessed at Weeks 0, 26 and 48 for participants in **Part 2** of the clinical trial only. Participants may opt out of this procedure.

### 12.2.1 ADDITIONAL VISITS

Additional visits and assessments may be required to evaluate an adverse event, and/or identify a diagnosis. These are compatible with the protocol.

The safety assessments are intense. Participants will be asked to remain in clinic for about 1 hour following each immunisation, and to complete a diary card until the day 7 safety visit. They will be advised to call the clinic staff if they are concerned, and 24 hour cover will be available.

Referral to an independent specialist with the appropriate expertise will be arranged if there is uncertainty about the relationship to vaccine.

### 12.2.2 VISIT WINDOWS

The second and third vaccination visits scheduled for weeks 12 and 24 will be compliant with the protocol if they take place -7 / +14 days either side of the target date determined by the date of the previous vaccination. If there is a delay >4 weeks a decision will be made by the TMG (see **section 20.1**) as to whether immunisation will continue.

The post-immunisation safety visits scheduled for weeks 1, 13 and 25 will be compliant with the protocol if they take place +/- 1 day of the target date determined by the date of the previous vaccination.

The primary endpoint visit (Visit 9; Week 26) and final safety visit scheduled for week 28 will be compliant with the protocol if they take place  $\pm$  2 days either side of the target date determined by the date of the third vaccination. The follow-up visit at Week 48 will be compliant with the protocol if it takes place  $\pm$ 14 days either side of the target date determined by the date of the third vaccination.

## 12.3 PROCEDURES FOR ASSESSING SAFETY AND TOLERABILITY

### 12.3.1 ADVERSE EVENT ASSESSMENT

Information on adverse events will be collected through questions at every visit from and including the enrolment visit up to week 28, as indicated in **Table 2**.

The investigator or delegate will record the diagnosis or the symptoms if a diagnosis is not apparent, the date of onset and the date of resolution if appropriate.

The relationship (to vaccine) and seriousness of the event will be determined by the investigator or delegate according to the definitions provided in **section 13.3**. All of this information will be recorded in the adverse event CRF.

### 12.3.2 PHYSICAL EXAMINATION AND VITAL SIGNS

The general and symptom-directed examinations, and assessment of vital signs will be performed at time points specified in **Table 2**. Additional physical examinations and vital signs assessments may be performed if indicated by the results of scheduled safety assessments.

### 12.3.3 ROUTINE SAFETY BLOODS AND URINE PREGNANCY

A pregnancy test will be performed by analysis of a urine sample for Human Chorionic Gonadotrophin (HCG) collected from female participants as detailed in Table 2. The analysis will be conducted by a member of the study team.

Peripheral blood will be collected and analysed for the following parameters at the time points specified in Table 2, and at additional time points if clinically indicated to further evaluate or follow up adverse events.

#### **Blood**

- Creatinine, ALT, alkaline phosphatase, total bilirubin
- Hb, total WBC, neutrophils, lymphocytes, platelets

### 12.3.4 SOLICITED LOCAL AND SYSTEMIC ADVERSE EVENTS

Various local and systemic adverse events are known to be associated with licensed vaccines, and are referred to as 'solicited adverse events'.

This information will be collected from all study participants on the day of immunisation and at the day 7 safety visit following each immunisation, through direct questions asked during a structured face to face interview and through examination according to the schedule.

Participants will also be asked to complete a diary card recording solicited adverse events that start from each immunisation until the day 7 safety visit.

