### 7.3 RESEARCH LEADING TO THE PROPOSAL OF CLINICAL STUDY

#### 7.3.1 ADENOVIRUS TYPE 4

Adenovirus serotype 4 belongs to the family of Adenoviridae, is frequently the causative agent for conjunctivitis or pharyngoconjunctival fever and is responsible for acute respiratory disease (ARD) among susceptible populations worldwide. Adenovirus serotype 4 is a non-enveloped, icosahedral virion, 70-90nm in diameter containing a double-stranded linear DNA genome. Adenovirus 4 transmission occurs through direct human to human contact, faecal-oral and occasionally water transmission.

The incubation period after transmission is between 1-10 days, and Ad4 infections vary in clinical manifestation and severity. Symptoms include fever, rhinitis, pharyngitis, tonsillitis, cough, or conjunctivitis. Usually a syndrome of fever, pharyngitis, and conjunctivitis (pharyngoconjunctival fever) is associated with an Ad4 infection. In addition, it has been documented that Ad4, the only known serotype of Adenovirus species E, is the leading causative agent of febrile respiratory infections (acute respiratory disease [ARD]) in military trainees. In rare instances, Ad4 has caused severe pneumonia in military recruits or immunocompromised individuals.

The Adenovirus serotype 4 parental vaccine protects against respiratory disease and is attenuated by the oral route of delivery. Previous studies of the oral replication competent Ad4 vector encoding hemagglutinin (HA) of H5N1 influenza have detected rectal, but not respiratory, shedding for up to 28 days after administration. Most importantly no shedding or evidence of seroconversion to the encoded transgene HA was observed in household contacts, but shedding was likely to be detected in vaccinees receiving the high dose of  $10^{11}$  VP after oral immunisation.

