**TABLE 3: SOLICITED ADVERSE EVENTS**

Type	Event
Local AEs (Immunisation site)	Pain Tenderness Erythema / Discolouration Warmth Itching Swelling
Systemic Clinical AEs	Abnormally raised temperature Chills / rigors Myalgia / flu-like general muscle aches Malaise Excess fatigue Headache Nausea / Vomiting Abdominal Pain Diarrhoea Sore throat

The events will be graded according to **Appendix 1**.

**Relationship to the product**, the assumption is that any of these solicited events starting within 7 days of an immunisation are at least possibly related. If the onset is beyond 7 days, the event will be recorded on the adverse event CRF and a relationship determined by the investigator or delegate.

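### Rhinitis, cough and conjunctivitis are not solicited, and solicitation stops at day 7, although the protocol's own account of Ad4 infection names all three and gives an incubation of up to 10 days

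*Protocol*

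**What the plan says.** Protocol section 7.3.1 describes Ad4 infection: "The incubation period after transmission is between 1-10 days, and Ad4 infections vary in clinical manifestation and severity". It continues: "Symptoms include fever, rhinitis, pharyngitis, tonsillitis, cough, or conjunctivitis". It then names the typical picture: "Usually a syndrome of fever, pharyngitis, and conjunctivitis (pharyngoconjunctival fever) is associated with an Ad4 infection". The same section adds that the parental vaccine is attenuated when given by mouth. It also reports that a related oral Ad4 influenza vector gave rectal but not respiratory "shedding for up to 28 days after administration".

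Table 3 solicits raised temperature, chills, myalgia, malaise, fatigue, headache, nausea or vomiting, abdominal pain, diarrhoea and sore throat, plus injection-site events. Rhinitis, cough and conjunctivitis are not on it. On timing, section 12.3.4 says: "Participants will also be asked to complete a diary card recording solicited adverse events that start from each immunisation until the day 7 safety visit". Structured questioning ends at the same visit. For later onsets of listed symptoms, the text under Table 3 says: "If the onset is beyond 7 days, the event will be recorded on the adverse event CRF", with relatedness then assigned by the investigator or delegate.

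Section 12.3.5 has all other events sought by a non-leading question. Table 4 automatically makes a solicited event an adverse reaction only if it starts within 7 days of vaccination. Section 10.2 leaves the clinical team unblinded throughout.

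**The concern.** Ad4-EnvCN54 is replication-competent, and section 7.8 says there are no clinical data for it. Its safety and tolerability is part of the primary objective, so one expects the solicited list and window to follow the protocol's own account of what the parent virus does. They do so only in part. Section 12.3.4 explains solicited events only as those known from licensed vaccines, and nothing explains why conjunctivitis is left out or why day 7 is the limit.

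Two things are at stake. The first is ascertainment: milder events of the unlisted kinds, and any event starting just after day 7, depend more on memory and on an open question. The second is classification. A listed symptom starting by day 7 becomes an adverse reaction automatically. An unlisted symptom, or a later onset, becomes one only if staff who know the allocation judge it related. Adverse-reaction status enters the primary endpoint of Grade 3-4 reactions (section 14.2.1) and the count of severe reactions in section 12.6.

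**Working it through.** The plan states no figure to reproduce. The check sets section 7.3.1 against Table 3 and counts days in Table 2.

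**Symptoms**

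| Named in section 7.3.1 | In Table 3? |
|---|---|
| Fever | Yes (raised temperature) |
| Pharyngitis | Yes (sore throat) |
| Tonsillitis | Only if read as sore throat |
| Rhinitis | No |
| Cough | No |
| Conjunctivitis | No |

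So 3 of 6 are missing if tonsillitis counts as sore throat, and 4 of 6 if it does not. Of the three parts of the usual syndrome, two are solicited and conjunctivitis is not.

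**Window.** Incubation runs over days 1 to 10. Solicitation to day 7 covers 7 of those 10 days. The day 7 visit has a window of ±1 day (section 12.2.2), so the diary may cover 6 to 8 of them. Nominally, days 8 to 10 fall outside.

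**Time to the next enquiry.** Doses are on days 0, 84 and 168; the relevant later visits are days 28, 112 and 182.

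- Dose 1: next visit after the day 7 visit is 28 − 0 = day 28 post-dose. For an onset on days 8 to 10 the gap is 28 − 8 = 20 to 28 − 10 = 18 days.
- Dose 2: 112 − 84 = day 28 post-dose, so the same 18 to 20 days.
- Dose 3: 182 − 168 = day 14 post-dose, so 14 − 10 = 4 to 14 − 8 = 6 days.

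For the three unlisted symptoms starting on days 0 to 7, the wait is short. Table 2 has unsolicited events asked about at the day 7 visit, so the open question comes within about a week.

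**Administrations affected by the long gap** (Table 1, six participants per group)

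- Dose 1: B, C, D, F, G, H = 6 × 6 = 36
- Dose 2: C, D, G, H = 4 × 6 = 24
- Dose 3: D, H = 2 × 6 = 12
- Total 36 + 24 + 12 = 72. Doses 1 and 2 make 60, and 60/72 = 83%.

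**Can the planned tables isolate the vector?** At Month 0 the only product is a capsule: Ad4 in 36 participants (B-D, F-H) and oral placebo in 12 (A, E). SAP section 12.2.2 splits Part 1 safety by arm where possible. Arm 1 is 6 placebo plus 18 Ad4 recipients at dose 1, and arm 2 is again 6 plus 18, so at that dose the two arms have the same mix. The arm split therefore says nothing about the capsule. Protocol section 14.5.4 does foresee results by group, so the contrast can be built, but neither document plans it. The first six Ad4 participants are pre-allocated (section 10.1.1), which leaves 36 − 6 = 30 randomised Ad4 recipients against 12 on oral placebo.

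**The case against.** The best defence is that section 7.3.1 describes natural infection after transmission. The same section calls the oral parental vaccine attenuated and reports no respiratory shedding with the related vector. Gastrointestinal replication is the expected behaviour, and Table 3 solicits nausea or vomiting, abdominal pain and diarrhoea. This stands as a possible reason for the choice, but the protocol does not give it. Whether a new construct behaves like the parental vaccine is also something a Phase I trial should observe.

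The second defence is that capture after day 7 is more than an open question. Table 2 adds symptom-directed examination and medication review at Weeks 4 and 16, and section 12.2.1 tells participants to call if concerned, with 24-hour cover. This stands. So does the point that Appendix 1 defines Grade 3 as preventing daily activity, which few would forget by day 28. The effect of recall on the primary endpoint is therefore probably small, and classification matters more. Even there, unlisted or late events can still be judged reactions under Table 5.

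A reader might infer more than the documents support:

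- *That most Ad4 illness goes unprompted.* Fever, sore throat and most general and gastrointestinal symptoms are solicited, over 7 of the 10 incubation days.
- *That 3 days in 10 means 30% of illness is missed.* That would need onset to be uniform over the incubation range, and no onset distribution is given.
- *That 28 days of shedding shows how much symptom collection is lost.* Shedding is a virological finding; it says nothing about when symptoms start.
- *That a positive Week 13 swab cannot be interpreted for want of a pre-dose swab at Week 12.* The schedule is: "Rectal swabs for Ad4-EnvCN54 PCR will be assessed at Weeks 0, 1, 4, 13, 16, 25, 26, 28 and 48". Groups B and F receive placebo capsules at Month 3 and show concurrently any persistence from dose 1; C and G do the same at Week 25. Every participant also has a swab about 28 days after doses 1 and 2.

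**Conclusion.** The mismatch is real but limited. Three of six named symptoms, one of them part of the usual syndrome, are never solicited. Any onset on days 8 to 10 is outside the window, and after 83% of Part 1 Ad4 administrations the next enquiry is 18 to 20 days after such an onset. Relatedness of these events rests on unblinded judgement.

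This matters for the new vector only in so far as natural-infection incubation and symptoms are a guide to it. The documents neither establish nor exclude that, so no share of missed illness can be given. It is an inexpensive improvement to a primary safety objective and does not show that the safety assessment is unsound.

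**What to change.** **If dosing continues.** Add conjunctivitis, rhinitis and cough to Table 3 and the diary card. Continue the diary to at least day 10 after every capsule, active or placebo, and review it at the next scheduled visit (Week 4, 16 or 26).

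**In the SAP.** Add one table of these events after dose 1, Ad4 (B-D, F-H) against oral placebo (A, E). Note that the first six Ad4 participants were not randomised, and show the result with and without them. Define the table's population as everyone who took a capsule. SAP section 9 defines the safety population by receipt of experimental vaccine; read literally, that drops anyone in A or E who stops before Month 3.

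**If dosing is complete.** The SAP is dated July 2021 and speaks of the trial's conduct in the past tense. In that case, build the dose 1 table from the recorded adverse events and state that solicitation ended at day 7 and omitted these symptoms.

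**In the protocol text.** Reconcile section 7.3.1 with section 12.3.4, Table 3 and Table 4, or give the reason for the difference. The reconciled text should say how events added to the list, or starting after day 7, bear on automatic attribution and on the section 12.6 count of severe reactions. That rule is for the trial team to decide.

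**Minor addition.** Sections 14.2 and SAP 10 list no shedding endpoint; a line for PCR positivity by visit and group would give the swabs a planned summary.

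**Cost.** Three diary lines, about three diary days and one table, with no new visit. More background colds will be recorded; the participant-blinded oral-placebo groups show how many to expect. If attribution were widened too, more events could count towards the section 12.6 hold, so that consequence must be settled at the same time.
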